Barrett's oesophagus (BO) is a common pre-malignant condition which is a risk factor for oesophageal adenocarcinoma (OAC) with a progression rate of 0.33% per annum. Surveillance endoscopy programmes have been widely adopted, without strong evidence, in the hope of detecting cases of OAC in the dysplastic or pre-invasion stage. Surveillance is costly both to the health service and to patients due to its invasive nature and psychological burden. Preliminary studies suggest current surveillance practice in the NHS is not meeting standards set out in the British Society of Gastroenterology (BSG) 2013 guideline.

This study aims to assess the efficacy of a dedicated BO surveillance service compared to current standards of practice. This research question was ranked 4th in a recent research priority setting exercise which engaged both research users and healthcare providers.

A randomised prospective pilot study is proposed. Patients with BO will be recruited prior to their surveillance endoscopy and randomly routed to either a dedicated BO endoscopy list or normal service list. Dedicated lists will be conducted by a gastroenterologist or nurse endoscopist with a specialist interest in BO. The control group will be the non-dedicated list which represent a real-world comparison and be undertaken by any JAG accredited endoscopist. For this pilot, measures of trial success will be used to judge it's efficacy to be expanded to a larger trial. The larger trial would then use the following outcome measures: 1) Clinical outcomes, including intestinal metaplasia, dysplasia and OAC detection rates. 2) Key endoscopic performance indicators outlined in the British Society of Gastroenterology (BSG) guidelines. 3) Patient centred outcomes, including Health related quality of life (HRQOL) measurement and patient satisfaction with services.

2 Study Team Roles and Responsibilities

2.3 Funding

Medtronic have agreed to fund this study with £33,469 over a two year period. This would be released in instalments according to agreement when the contracts have been completed. The proposed instalments from Medtronic would be £5000 after signing of the contract, £10,000 1 year from contract execution, £15,000 after year 2 and £3,469 at publication of the results.

The incidence of gastroesophageal reflux disease and Barrett's oesophagus is rising, as a direct precursor to oesophageal adenocarcinoma (OAC) this has huge implications on the population⁽¹⁾. Currently outcomes for OAC are still extremely poor with a less than 13% five year survival overall for cases after invasion⁽²⁾. Though there have been no randomised controlled trials supporting surveillance (awaiting output from the Barrett's Oesophagus Surveillance versus endoscopy at need Study(BOSS) trial⁽³⁾), retrospective studies have shown surveillance can increase the number of cases which are discovered at an earlier stage where other modalities of treatment can be utilised. This has led to the development of BO surveillance guidelines in both Europe^(4,5) and the US ^(6,7). The efficacy of endoscopic therapy for dysplasia and early OAC is now well established with increasingly durable long-term data ⁽⁸⁾. One major difficulty with BO is identifying those at risk of disease progression. Considering current research into individual risk stratification is likely to take years to reach routine clinical use surveillance endoscopy remains best practice for detecting changes. A number of studies have focused their efforts on advanced endoscopic modalities to detect dysplasia more readily, with mixed results. One major issue with these techniques is the transferability out of tertiary centres and the additional training or equipment required⁽⁹⁾. In the meantime, we have limited knowledge of current surveillance practices across the UK.

Firstly, a prior literature review of HRQOL in BO and an exploratory qualitative study, have highlighted key areas of BO disease impact^(11,12). The latter also found a significant discrepancy between patient follow up experiences and engagement of professionals to address it. In particular patients sought enhanced communication, structure and continuity of

care. They clearly valued interaction with a specialist and the concept of direct access to a dedicated service in-between endoscopy was reassuring to them.

Secondly, a single centre cohort study demonstrated that a dedicated list adhered more closely to the BSG guidelines when compared to current and past non-dedicated endoscopies respectively⁽¹³⁾; Prague classification (100% vs 87.3% vs 82.5%, p<0.0001), hiatus hernia delineation (100% vs 64.8% vs 63.3%, p<0.0001), location and number of biopsies recorded (99.5% vs 5.6% vs 6.9%, p<0.0001), Seattle protocol adherence (72% vs 42% vs 50%, p<0.0001) and surveillance interval adherence (dedicated 100% vs prior endoscopy 75%, p<0.0001).

These preliminary qualitative and quantitative studies suggest the post-BSG guideline era of BO surveillance remains suboptimal in terms of patient needs and current best practice metrics. A dedicated service could be a means to improve the accuracy and consistency of surveillance care, although it remains unclear whether such a service can consistently improve clinical and patient centred outcomes. Although other studies from single centre audits show promise, we believe a randomised blinded study will provide the most robust evidence. This approach will eliminate bias in assignment and generate prospective data for robust analysis. We acknowledge this will carry challenges in design and implementation therefore we propose a pilot study to test whether a randomised prospective, multicentre study is feasible.

5 Aims of the proposed research

Primary Objective:

- To assess the feasibility of a randomised controlled trial comparing a dedicated endoscopy service for Barrett's surveillance verses current normal practice
- To assess the feasibility of collecting data for the below:
- Adherence to best practice guidelines for Barrett's oesophagus surveillance and upper GI endoscopy.
- Clinical outcome measures, including dysplasia and OAC diagnosis rates.
- Patient centred outcome measures, including satisfaction with services and health related quality of life.

6 Study Design

Design: A prospective, pilot randomised controlled trial.

Setting: This study will be conducted solely within the UK NHS and is designed to reflect and compare against real world practice. The Initial site to open will be Northern Care Alliance NHS Foundation Trust (NCAFT) as they have an established dedicated service which will allow ease of study initiation. Once this is established we can possibly open Wrightington Wigan and Leigh NHS trust as there is a full time clinical research fellow running a dedicated service there. This will be part of the pilot as it will allow us to test the feasibility of running the study in more than one site.

Methodology and Recruitment;

Each site will have a dedicated Barrett's endoscopy list which we expect to be run by a research fellow, consultant or nurse endoscopist with a special interest in BO. This is defined by a self-declared interest and regular experience of performing surveillance. The list should be scheduled appropriately and include only Barrett's patients. The non-dedicated lists any other list performed by an endoscopist who is accredited by the Joint Advisory group to perform upper GI endoscopy who does not have a specialist interest in Barrett's and does not

attend upper GI multidisciplinary meetings. All endoscopists must be accredited in diagnostic gastroscopy by the Joint Advisory Group (JAG). Both study arms will be expected to use high definition white light endoscopy as outlined in the BSG guidelines. Use of further imaging modalities, such as narrow band imaging, will be at the discretion of the endoscopist on a case by case basis, this is in line with their current usual care outside of the research study.

Participants will be identified from hospital booking databases and invited to participate around 6-8 weeks prior to their planned surveillance endoscopy. If they would like to be involved in the study they may be invited to attend a meeting or receive a telephone call with one of the study team, to discuss any concerns and then be recruited with either written consent or may be asked to complete consent over the telephone, for example in situations where to protect the safety of the participant and staff, it is not appropriate to bring the participant into a clinical setting for the consent process (e.g during the COVID-19 pandemic).

The participants will be randomly allocated either to the dedicated service or to any other endoscopy list performed by a JAG accredited upper GI endoscopist (current normal care). The endoscopists will all be blinded to the participant's involvement in the study. The randomisation will be performed by the clinical trials assistant and the appointments made on an appropriate list by the endoscopy booking team. The participants will not be informed of which list they are allocated and they will receive an appointment as per their usual surveillance. The justification for blinding the participants is that this will avoid bias in their completion of the post-endoscopy questionnaire. Blinding the endoscopists aims to avoid a trial effect eq. a change in practice such as better adherence to the guidelines. This will be achievable as both study sites have a dedicated service established, the study will not significantly alter from normal care as Barrett's surveillance cases often are routed to different lists due to availability and timing.

Following the endoscopy, all participants will be asked to complete a Health related quality of life (HRQOL) guestionnaire around the time of their surveillance test, this is not part of their routine care and is for the research study only.

Key endoscopic performance data and clinical data will be collected prospectively;

Key endoscopic performance data

- BSG endoscopic reporting dataset for BO surveillance
- \triangleright Hiatus hernia delineation (cm between diaphragmatic pinch and top of gastric folds)
- Prague classification (CnMn) \triangleright
- \triangleright Visible island description (size and distance from incisors)
- Visible lesion description (Paris classification)
- AAA Seattle protocol biopsies (number and distance from incisors)
- Other performance data
- Oesophageal withdrawal time
- Comfort scores
- ≻ Sedation rates
- Intestinal metaplasia, dysplasia and OAC at histology

Clinical Data

- Participant demographics including potential confounding factors such as co- \geq morbidities, smoking status, BMI and family history of OAC.
- ≻ Seattle protocol adherence (histology reported biopsy numbers)
- ≻ Surveillance interval adherence
- ≻ Histology results (intestinal metaplasia, dysplasia and OAC)
- Discharges from surveillance

[figure not shown]
HRQOL measurement

As there is no validated patient reported outcome measure for Barrett's oesophagus we plan to use a number of measures based on our prior literature review and qualitative research. These will likely include a generic QOL measurement tool (e.g. the Short Form 36), worry of cancer assessment (cancer worry scale), a symptom measure (e.g. gastrointestinal symptom rating scale) and assessment of psychological burden (e.g. Hospital anxiety and depression scale).

Statistical analysis

As this is a pilot study descriptive statistics will be used to analyse measures of study success. These will include aspects like recruitment rates, retention of participants, ease of randomisation, drop-out rates and data completion. The study size will be 100 participants for a pilot study based on previously recorded optimum study sizes for feasibility/pilot studies.

6.1 Flow Diagram

7 Detailed Plan of Investigation

7.1 Recruitment procedure

Participants who are due to be attending for their scheduled Barrett's surveillance will be identified from a local database by the chief investigator, principle investigator, research fellow or research nurses as part of the clinical care team. Potential participants will be contacted with an invitation letter alongside a participant information sheet and informed consent form by post inviting them to participate in the study. If a participant contacts the study team interested in participating they may be invited to meet one of the study team in person to go through the written consent and check their capacity to be in the study, this will be a stand-alone meeting separate from their usual care as they would not usually be seen in clinic prior to their surveillance test. Or in some circumstances the participant may be asked to complete consent over the telephone. For example, in situations where to protect the safety of the participant and staff, it is not appropriate to bring the participant into a clinical setting for the consent process (e.g. during the COVID-19 pandemic). They will be randomly routed to a dedicated or non-dedicated endoscopy list for their surveillance and will not be informed of which they will be attending. The participants will be consented for the fact that they will not know which arm they are attending and the reasoning behind this.

7.2 Study protocol

7.2.1.1 Inclusion/Exclusion Criteria

Eligibility for inclusion/exclusion will be decided by the consenting clinician.

Inclusion Criteria:

- Must have capacity to give informed consent
- >18 years old. No upper age limit.
- Meet the diagnostic criteria for Barrett's Oesophagus without dysplasia prior to this endoscopy:
 - Non-Dysplastic Barrett's Oesophagus. All patients enrolled in surveillance who have been given a diagnosis of BO irrespective of current histology (lack of intestinal metaplasia on latest biopsies is not a criterion for exclusion providing future surveillance is indicated/recommended)

Exclusion Criteria:

- Lacks capacity to give informed consent
- Less than 18 years old

7.3 Study duration

	Year 1				Year 2			
Activities	Q1	Q2	Q3	Q4	Q1	Q2	Q3	Q4
Phase 1 – opening initial site at NCAFT								
Phase 2 – opening WWL, recruitment and randomisation of participants								
Phase 3 – Data cleaning and analysis								
Phase 4 – Final data reporting and dissemination								

Monitoring 1 – Site visits	*	*	*	*	*		*	
Monitoring 2 – teleconferencing with study sites		*	*	*	*	*	*	*

7.5 Consent procedure

Participants will be approached via letter of invitation or telephone call. They will be sent a Participant information sheet (PIS) and Informed Consent Form (ICF) and then if interested in participating they can contact the study team or will have a follow up phone call to see if they are interested. If they would like to be involved they may either be invited to meet or have a telephone call with one of the study team to be allowed to ask questions, go through the consent procedure and be informed of their right to withdraw at any stage. This meeting/telephone call will be separate from their normal care as they would not usually be seen prior to their surveillance test in clinic. If consent is via telephone, the researcher will use a telephone script/consent form to ensure the process is documented appropriately. The contact will include a clear verbal explanation of the study (e.g. by talking through the PIS and II the sections of the ICF. Only when the potential participant has had the opportunity to ask questions and had these answered satisfactorily, will he/she be asked to verbally confirm consent to participate. The telephone consent will be documented by the researcher/consent taker.

They will be informed that they will be randomised to normal practice or a dedicated service endoscopy and given a questionnaire about their care before and afterwards. They will be made aware that they will not be told which list they are attending and that so far there is no evidence of either being superior to avoid any concerns. They will be made aware of the distribution plan and that their data will be anonymised and safely stored and that they can be informed of the outcome of the study. They will be informed that at any stage if they wish to withdraw from the study this will have no effect on their ongoing NHS care.

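### Section 7.5 has participants told that no evidence favours either list, but the protocol's own background reports closer guideline adherence on the dedicated list

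*Protocol*

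**What the plan says.** Protocol section 7.5 (Consent procedure) lists what participants will be told. They will be randomised between usual practice and a dedicated service, they will not learn which list they attend, and "so far there is no evidence of either being superior to avoid any concerns". The sentence does not say superior in what respect, and the purpose it gives is reassurance.

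The background, in the text leading up to section 5, says that "a single centre cohort study demonstrated that a dedicated list adhered more closely to the BSG guidelines". Its figures set the dedicated list against two other groups, first current and then past non-dedicated endoscopies. For biopsy practice the result is "Seattle protocol adherence (72% vs 42% vs 50%, p<0.0001".

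Three further measures carry the same p-value:

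- recording of biopsy site and count: dedicated 99.5%, current 5.6%, past 6.9%
- measurement of any hiatus hernia: dedicated 100%, current 64.8%, past 63.3%
- use of the Prague system: dedicated 100%, current 87.3%, past 82.5%

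The fifth measure has one comparator only: "surveillance interval adherence (dedicated 100% vs prior endoscopy 75%, p<0.0001".

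The background adds that audits from other single centres are promising. It then states what is still open: "it remains unclear whether such a service can consistently improve clinical and patient centred outcomes".

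The opening summary gives the larger trial three outcome domains: clinical outcomes, endoscopic performance indicators from the national guideline, and patient-centred outcomes. Section 5 includes guideline adherence among the data whose collection the pilot will test. Sections 6, 7.6 and 10 all name recruitment rate as a measure of study success.

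**The concern.** The background confines the uncertainty to clinical and patient-centred outcomes. Section 7.5 turns this into a general denial that any evidence exists. For guideline adherence, one of the larger trial's own outcome domains, that denial conflicts with what the protocol reports a few pages earlier.

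Two things are at stake. The first is the accuracy of consent. The background says patients in earlier qualitative work valued contact with a specialist and were reassured by the idea of a dedicated service, so the information is of a kind they may want to weigh. Because they will not be told their list, the consent discussion is where they can do so.

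The second is what the pilot's recruitment rate means. It is collected to judge whether a larger trial is feasible. If that trial describes the evidence accurately, a rate obtained under the present statement answers a somewhat different question.

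**Working it through.** The point is a conflict between two parts of one document, so the check is whether both can stand. No sample size or power figure depends on it.

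**Step 1: direction and size of the reported evidence.** Inputs are the percentages in the background. Difference = dedicated minus non-dedicated, in percentage points.

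| Measure | Versus current non-dedicated | Versus past non-dedicated |
|---|---|---|
| Prague classification | 100 − 87.3 = 12.7 | 100 − 82.5 = 17.5 |
| Hiatus hernia delineation | 100 − 64.8 = 35.2 | 100 − 63.3 = 36.7 |
| Biopsy location and number recorded | 99.5 − 5.6 = 93.9 | 99.5 − 6.9 = 92.6 |
| Seattle protocol adherence | 72 − 42 = 30.0 | 72 − 50 = 22.0 |
| Surveillance interval adherence | not given | 100 − 75 = 25.0 (prior endoscopy) |

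All nine differences favour the dedicated list.

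**Step 2: can the p-values be reproduced?** No. The protocol gives neither the group sizes nor the test. Four of the five p-values appear once beside three groups, so pairwise results are not shown. The fifth compares with prior endoscopy only.

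A plausibility check is possible if two independent groups of equal size are assumed. With a pooled two-proportion z-test, d the difference and p̄ the mean of the two proportions, the smallest n per group for two-sided p<0.0001 is

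n = z² × 2p̄(1 − p̄) / d², with z = 3.891 and z² = 15.14.

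For Seattle against current lists, p̄ = (0.72 + 0.42)/2 = 0.57, so n = 15.14 × 2 × 0.57 × 0.43 / 0.30² = 82.5, rounded up to 83. In the same way:

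- Prague: 112 (current), 79 (past)
- Hiatus hernia: 36, 34
- Biopsy recording: 9, 9
- Seattle: 83, 149
- Surveillance interval: 53 (prior endoscopy)

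Groups of roughly 150 each would therefore be enough for every stated p-value. They are plausible, but not verified.

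**Step 3: the statements side by side.**

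| | Guideline adherence | Clinical and patient-centred outcomes |
|---|---|---|
| Background | Cohort evidence favours the dedicated list | Unclear |
| Section 7.5 | No evidence either way | No evidence either way |

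The right-hand column is broadly consistent. The middle column is not.

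**The case against.** The strongest reply is that section 7.5 is a loose lay statement of equipoise. On this view, superior means better for the patient, and on that the protocol is openly uncertain. The evidence is observational and from one centre. Three of the five measures concern what was documented, and the largest gap, 93.9 points, is in recording biopsies, which is neither taking them nor benefiting from them. This limits how much weight the evidence can bear. It supports calling the evidence preliminary and non-randomised, but not saying there is none, and the sentence carries no qualifier that would produce the narrower meaning.

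Other objections stand and mark where a reader might go too far:

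- **That all participants would consent on this wording, with the adherence results withheld.** The information sheet, consent form and telephone script are not shown and may describe the cohort. Only the message prescribed in section 7.5 can be criticised.
- **That the pilot will overstate recruitment.** The direction is not established. Some patients might decline if told of the cohort. Others might join for a chance of the dedicated list, since section 6 says surveillance cases already go to different lists according to availability.
- **That the dedicated list beat its actual comparator on every measure at p<0.0001.** The interval measure has no current non-dedicated figure, and pairwise tests are not reported for the other four.
- **That the trial lacks equipoise.** The background's stated uncertainty on clinical and patient-centred outcomes is not contradicted.
- **That a larger trial would have to disclose this pilot's results.** Nothing in the protocol says so.

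It is also true that no randomisation step or analysis depends on this sentence, and that ethics approval is required before the study starts (section 8.1). Neither makes the sentence consistent with the background.

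**Conclusion.** The concern holds in a limited form. Section 7.5 prescribes a consent statement that the protocol's own background contradicts for guideline adherence, an outcome domain of the planned larger trial. The evidence passed over is five process measures, all favouring the dedicated list, by 12.7 to 93.9 points against current lists on the four measures that have that comparison. It comes from one non-randomised cohort, with p-values that cannot be checked from the protocol.

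The consequence for the pilot is that its recruitment rate may not transfer to a trial that describes the evidence accurately. The size and sign of that effect are unknown. The inaccuracy of the statement does not depend on it. How far the wording reaches participants depends on whether the information sheet and telephone script follow section 7.5.

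**What to change.** Reword section 7.5 to say that an earlier non-randomised study at a single centre found closer adherence to national guidelines on dedicated lists, and that it is not known whether this improves clinical outcomes or outcomes that matter to patients. Check the information sheet and telephone script, and make the same change if they carry the present message. Nothing beyond what the background already states is needed.

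Add a field for reasons for declining, where patients offer them, to the screening log that section 9 already requires for all eligible patients approached. This will help in interpreting the recruitment rate. If recruitment has begun, report uptake before and after the change separately.

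The cost is an amendment to the protocol and possibly to participant documents, with sponsor agreement and ethics review under section 8.2. Uptake may change in either direction, but the rate then obtained will be more relevant to the larger trial.
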